### 10.3.3 Exploratory Objectives

To compare MRD results over time by PCR, correlational analyses such as McNemar's test, Pearson and Spearman correlations and Lin's concordance statistics will be used, depending on the metric for MRD (as detected by either flow cytometry or by PCR) used in the analysis. To correlate MRD with either PFS or OS, proportional hazards regression with a time dependent covariate (MRD) will be used.

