### 2.3 Exploratory Objectives & Endpoints

Compare MRD results overtime by PCR and correlate these with PFS and OS.

We will obtain archived tissue (FFPE slides) from a previous biopsy from all patients for baseline clone identification; in addition, we will collect peripheral whole blood samples at baseline, 1 month after first dose, 6 months after first dose, and approximately 18-24 months after first dose. MRD analysis will be

Study Numbers: NU 14H06  
PCI-32765MCL2003Initial version: September 24, 2014  
AMD 11: ver. date 08.06.2022

conducted using PCR methods and results will be compared over time and correlated with PFS and OS.

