### **9.0 EXPLORATORY STUDIES**

MRD analysis will be conducted using PCR methods and results will be compared over time (four time-points total). In addition, we will correlate results with PFS and OS. At Northwestern University, the Pathology Core Facility (PCF) Clinical Trials staff will be responsible for procuring, processing, and shipping all samples (tissue and peripheral blood) for exploratory studies. Participating sites should use whatever local services they have available to handle this aspect.

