#### **9.1.2 Peripheral Blood**

Three peripheral blood samples for exploratory studies will be collected at baseline (prior to treatment on Cycle 1 Day 1), after 1 month of treatment, 6 months of treatment, and approximately 18-24 months post-first dose of treatment. All study blood samples will be collected at the same time as blood is being drawn for routine care/tests. Two samples will be collected using lavender-top EDTA Vacutainer® sample collection tube. Label the tube with the date of the draw, patient ID number, and patient initials. Using the labeled, lavender-top EDTA Vacutainer® sample collection tube, approximately 10cc of blood will be drawn. Tubes should be gently inverted 8 times to ensure adequate mixing of the anticoagulant. Blood samples may be stored at ambient temperature for up to 24 hours.

Within 24 hours of sample collection, perform cell preparation using Ficoll protocol on one of the EDTA tubes. Isolate peripheral blood mononuclear

cells (PBMCs). Store PBMCs at -80C until shipment (see lab manual for details).

For the second sample of peripheral blood, flow cytometry will be performed, as standard of care at the treating institution. The results of the flow cytometry will be interpreted as positive or negative per the treating investigator and recorded for comparison with simultaneous results of MRD testing by PCR.

A third optional sample will be collected in a 6mL EDTA tube for future research that involves evaluating the treatment response by analyzing changes in the proportion of tumorigenic clones within the patient's blood as compared to the initial biopsy. These samples will be stored in PCF Clinical Trials Unit (CTU). Such future research must be reviewed and approved by Janssen prior to use of the samples.

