### **10.1.3 Exploratory Endpoints**

Minimum residual disease (MRD) will be quantified as being either categorical or continuous.

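### For continuous MRD, none of the statistics named in section 10.3.3 for comparing PCR results over time estimates the direction or size of change.

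*Combined protocol and SAP*

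**What the plan says.** The exploratory objective in section 2.3 reads "Compare MRD results overtime by PCR and correlate these with PFS and OS". Sections 2.3 and 9.0 plan four blood samples per patient: before treatment, at about 1 month, at about 6 months, and at about 18 to 24 months after the first dose.

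The measurement scale is left open. Section 10.1.3 says "Minimum residual disease (MRD) will be quantified as being either categorical or continuous".

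For the comparison over time, section 10.3.3 gives an open list of examples, which it calls correlational. McNemar's test comes first; the list then continues "Pearson and Spearman correlations and Lin's concordance statistics will be used", with the choice "depending on the metric for MRD (as detected by either flow cytometry or by PCR) used in the analysis". It names no reference time point, no pairs of time points and no estimate of change. Its other sentence, proportional hazards regression with MRD as a time-dependent covariate, serves the separate aim of relating MRD to PFS and OS.

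Section 9.1.2 adds a second comparison, flow cytometry against PCR at the same visit. "The results of the flow cytometry will be interpreted as positive or negative per the treating investigator", and those results are "recorded for comparison with simultaneous results of MRD testing by PCR".

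**The concern.** Comparing MRD over time during maintenance means asking whether MRD went down, stayed level or went up, and by how much. A correlation between baseline and a later sample asks something else: whether patients who start high also end high. An agreement coefficient asks whether the two readings coincide. Neither returns a signed change.

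If MRD is reported quantitatively and the named statistics are followed, a high Pearson or Spearman coefficient could be reported equally for a drug that lowered MRD tenfold in every patient and for one that left it unchanged. A reduced Lin coefficient could mean improvement or worsening. MRD is the only exploratory objective, and samples are planned for all patients, so these data should be analysed with a method that can answer the question.

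**Working it through.** The plan gives no sample size, effect size or error rate for the MRD analysis, so there is no figure of its own to reproduce. The check concerns the properties of the named statistics.

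**Set-up (assumed values, not from the documents).** Let x be baseline log10 MRD with variance 1. Let y = x + e + d be the later value, where e is independent noise with SD 0.3 (variance 0.09) and d is a uniform shift. Then var(y) = 1 + 0.09 = 1.09 and cov(x, y) = 1, whatever d is.

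**Pearson.** r = cov / sqrt(var x × var y) = 1 / sqrt(1.09) = 0.96. The shift d does not appear in the formula.

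**Spearman.** Adding a constant to every y leaves the ranks unchanged, so d has no effect here either.

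**Lin.** CCC = 2 cov / (var x + var y + d²). The shift enters only as a square, so its sign is lost.

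| Shift d (log10) | Pearson | Lin |
|---|---|---|
| −1 (tenfold fall) | 0.96 | 2 / 3.09 = 0.65 |
| 0 | 0.96 | 2 / 2.09 = 0.96 |
| +1 (tenfold rise) | 0.96 | 2 / 3.09 = 0.65 |

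**Second set of assumptions.** One simulated set of 36 pairs (36 is the evaluable sample size in section 10.2) used a baseline mean of −3 and SD of 1 log10, with noise SD 0.5. Paired-change methods were run on the same data.

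| Shift d | Pearson | Spearman | Lin | Mean change | Signed-rank p |
|---|---|---|---|---|---|
| −1 | 0.921 | 0.839 | 0.584 | −1.0 | 3 × 10⁻¹¹ |
| 0 | 0.921 | 0.839 | 0.921 | 0.0 | 0.90 |
| +1 | 0.921 | 0.839 | 0.584 | +1.0 | 3 × 10⁻¹¹ |

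The pattern is the same. The mean change separates the three cases; the correlations do not, and Lin separates only change from no change.

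**McNemar for positive/negative MRD.** Take 12 discordant pairs among 36 patients (illustrative counts). The exact two-sided p for a 10:2 split is 2 × (66 + 12 + 1) / 4096 = 0.039.

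- 10 positive-to-negative and 2 negative-to-positive: p = 0.039, net change −8/36 = −22 percentage points.
- 6 and 6: p = 1.0, net change 0.
- 2 and 10: p = 0.039, net change +22 percentage points.

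With the discordant counts reported, McNemar shows direction. It takes two time points at once. Four time points give three comparisons against baseline, or six pairs in all, and the plan does not say which are meant.

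**The case against.** **McNemar's test is listed first.** This stands. A reader might infer that the whole plan for MRD over time is blind to change, and the documents do not support that. If MRD is read as positive or negative, the plan has a test of change. The gap is confined to continuous MRD.

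**Lin's coefficient registers a shift.** It does: 0.65 against 0.96 above. What it loses is the sign. The two means used to compute it would supply the direction, but the plan does not ask for them to be reported.

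**Clearance would not look like no effect.** A reader might infer that the planned statistics could not tell disease clearance from an inactive drug. That goes too far, because the calculation models a uniform tenfold fall with values still measurable. Keep SD 1 and noise 0.3, and add an assumed baseline mean of −3 log10 and a detection floor of −5 log10. With 83% of patients undetectable at follow-up, Pearson drops to 0.60 and Lin to 0.07. With 97% undetectable they are about 0.3 and 0.01. If every patient clears, Pearson is undefined.

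**Agreement statistics have a proper use for PCR versus flow.** This also stands. A reader might infer that Lin's coefficient never suits that comparison because flow is binary. If PCR is also read as positive or negative, Lin's coefficient (computed with divisor n) equals Cohen's kappa exactly and Pearson is the phi coefficient. The mismatch arises only for continuous PCR against binary flow.

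**The list is open, and quantitative MRD may not exist.** The wording of 10.3.3 does not forbid a paired comparison. Assay details sit in a separate lab manual, so whether PCR results will be quantitative is unknown. But every continuous-data example offered measures association or agreement, and an open list does not prespecify a measure of change. Nor were the statistics introduced only for PCR versus flow: 10.3.3 assigns them to PCR over time, and Appendix IV shows the list was there before Amendment 1 added the reference to flow.

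**Conclusion.** The point holds for continuous MRD. Of the statistics named in 10.3.3, Pearson and Spearman are unchanged by a uniform shift and Lin's coefficient is symmetric in its direction, so none estimates the direction or size of change. This follows from the formulas. Only the illustrative values (0.96, 0.65 and the simulated figures) depend on the assumed SDs, and the simulated figures come from a single data set.

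For positive/negative MRD, McNemar's test addresses change, but only between two time points at a time. No reference time point or handling of multiplicity across the four samples is stated.

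The consequence is small. MRD is exploratory, no decision rule uses it, and its relation to PFS and OS has its own method. The primary three-year PFS conclusion is unaffected. This is a worthwhile improvement rather than a necessary correction.

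**What to change.** Rewrite the first sentence of 10.3.3 so that the two aims are separate.

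- **Change over time, quantitative MRD.** Estimate change from baseline on log10 MRD at each later time point, with a Wilcoxon signed-rank test or a mixed model with time as a factor. State a rule for undetectable values, for example ranking them lowest in a rank-based analysis or treating them as left-censored at the detection limit in a model. The rule matters because all patients enter in CR or PR and log10 of an undetectable result has no value.
- **Change over time, positive/negative MRD.** Use exact McNemar against baseline at each later time point, and report the discordant counts.
- **Multiplicity.** Label the three comparisons against baseline as exploratory, or adjust them.
- **PCR versus flow at the same time point.** Keep agreement statistics here. Use kappa for two binary results, which is the same number as Lin's coefficient in that case.

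The cost is one paragraph and a detection-limit convention to agree before MRD is analysed. It needs no new samples, visits or patients, and the analysis time is negligible.

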### 10.3.4 Interim Analysis

Patients will be formally evaluated for an interim safety analysis as described below after 15, 20 and 25 patients have been observed. The PI along with the Northwestern Lymphoproliferative Disorders disease team and Quality Assurance will assess data to ensure there are no unexpected safety signals that have been observed at this time.

Serious adverse event (SAE, Section 7.2.3) assessment will be done using a Pocock-type boundary [16]. With 36 patients, if the **drug-related** SAE rate is **25%**, and there is a 5% probability of detecting an excess of SAEs when the SAE rate is at most 25%, then the number of SAEs that need to be observed as the trial progresses in order to detect an excess of SAEs are 9 SAEs/15 patients, 10/20 or 12/25. The boundary can be calculated for any interim sample size.

With 36 patients, if the drug-related Grade 5 SAE rate is 1%, and there is a 5% probability of detecting an excess of Grade 5 SAEs when the SAE rate is at most 1%, then using the Pocock-type boundary, the number of Grade 5 SAEs that need to be observed as the trials progresses in order to detect an excess of Grade 5 SAEs are at least 2 if the current sample size is 26 or less, and at least 3 if the current sample size is between 27 and 36.

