### 6.2 Secondary Endpoints

#### 6.2.1 Toxicity

All patients who receive at least one dose of ibrutinib will be evaluable for toxicity (including those who are replaced for efficacy endpoints). The study will use the CTCAE version 4.03 (see appendices for link) for reporting of adverse events. The occurrence and severity of each will be recorded.

After the study has been opened for 18 months, patients will be evaluated for an interim safety analysis. The PI along with the Northwestern Lymphoproliferative Disorders disease team and Quality Assurance will assess data to ensure there are no unexpected safety signals that have been observed at this time. See section 10.3.4 for details on the safety analysis.

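### The SAE boundary's stated 5% fits a check after every patient to 36, but Section 10.3.4 schedules looks only at 15, 20 and 25 (1.8% if those are all), and Section 6.2.1 names an 18-month look instead

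*Combined protocol and SAP*

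**What the plan says.** Section 10.3.4 (Interim Analysis) sets a Pocock-type boundary for drug-related SAEs, with 36 patients and a reference rate of 25%. Its stated property is that "there is a 5% probability of detecting an excess of SAEs when the SAE rate is at most 25" per cent. It describes the limits as "the number of SAEs that need to be observed as the trial progresses" and prints "9 SAEs/15 patients, 10/20 or 12/25". It adds: "The boundary can be calculated for any interim sample size".

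On timing, the same section says that the formal evaluation takes place "after 15, 20 and 25 patients have been observed". It names no other look. For Grade 5 SAEs it prints a limit of 2 up to 26 patients and "at least 3 if the current sample size is between 27 and 36".

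Section 6.2.1 (Toxicity) has a different timing: "After the study has been opened for 18 months, patients will be evaluated for an interim safety analysis". It then points to the statistics section: "See section 10.3.4 for details on the safety analysis".

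**The concern.** The false-flag probability of a sequential boundary depends on how often it is checked. The 5% in 10.3.4 therefore means nothing until the looks are fixed, and the current text supports three schedules: the three named sample sizes, continuous checking, and one calendar look at 18 months.

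If the investigators and quality assurance staff follow the scheduling sentence literally, they apply a weaker rule than the 5% implies and make no formal SAE comparison after patient 25, although 11 more patients are planned (36 − 25). The cost is a lower chance of noticing a true excess.

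**Working it through.** **Inputs.** From 10.3.4: reference rate p = 0.25; stated probability 5%; limits 9, 10 and 12 at n = 15, 20 and 25; maximum 36 patients. Assumed: each patient contributes at most one counted event, known when the patient is counted.

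**Method.** Let f(n, s) be the probability that s of the first n patients have an event and no limit has been reached. Then f(n+1, s) = (1 − p)·f(n, s) + p·f(n, s − 1). At each look, the mass with s at or above the limit is removed and added to the flagging probability. A Pocock-type boundary uses, at every look, the smallest r with P(X ≥ r | n, p) ≤ a. The common level a is the largest that keeps the overall probability at or below 5%.

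**Step 1: reproduce the printed limits.** Single-look tails at p = 0.25:

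| n | printed limit r | P(X ≥ r) | P(X ≥ r − 1) |
|---|---|---|---|
| 15 | 9 | 0.0042 | 0.0173 |
| 20 | 10 | 0.0139 | 0.0409 |
| 25 | 12 | 0.0107 | 0.0297 |

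Any a from 0.0139 up to just below 0.0173 gives exactly these limits. Searching with a check after every patient from 1 to 36 gives a = 0.0155 and an overall probability of 4.73%. The next attainable level, 0.0156, gives 5.96%. The printed limits and the stated 5% thus agree under checks after every patient; the gap between 4.7% and 5% is discreteness.

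**Step 2: apply the same limits only at the scheduled looks.** The sum of the three tails is an upper bound: 0.0042 + 0.0139 + 0.0107 = 0.0288, already below 5%. The exact first-crossing probabilities are 0.0042 at 15, 0.0105 at 20 and 0.0038 at 25. Their sum is 0.0184 from unrounded values, or **1.8%**. A Pocock-type search over these three looks would give different limits: 8/15, 10/20 and 11/25, with 3.9% overall.

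**Step 3: probability of flagging.** The true rates of 40 to 50% are chosen for illustration; the plan names no rate that it wants to detect.

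| Rule | 25% (false flag) | 40% | 45% | 50% |
|---|---|---|---|---|
| Printed limits at 15, 20, 25 | 1.8% | 32% | 51% | 70% |
| Same, plus 16 at n = 36 | 2.2% | 42% | 65% | 83% |
| 8/15, 10/20, 11/25 | 3.9% | 44% | 64% | 80% |
| After every patient to 36 | 4.7% | 51% | 72% | 87% |

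**Step 4: counting unit.** The limits are worded in SAEs, while the calculation needs patients with an SAE. If 10% or 20% of affected patients have a second drug-related SAE (assumption) and events are counted, the false-flag probability at the three looks becomes 6.0% or 11.6%. After every patient it becomes 13.2% or 22.7%. Either way it exceeds 5%.

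**Step 5: the 18-month look.** Section 10.3.4 contains no calendar look, so the cross-reference from 6.2.1 leads nowhere. For scale, Section 3.0 anticipates at least 2 patients per month once all sites are enrolling. If exactly 2 per month held from opening (assumption), patient 25 would enter at 25/2 = 12.5 months and patient 36 at 36/2 = 18 months, so the calendar look would coincide with none of the three. Slower early accrual would move this, but the two sections conflict at any accrual rate.

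**The case against.** The strongest reply is that continuous monitoring was intended and no number is wrong. The limits fit it, the section speaks of the trial progressing and of any interim sample size, and the Grade 5 rule is written by current sample size through 36. The Amendment 5 entry in Appendix IV also calls the monitoring continuous, which is evidence of intent only. Much of this stands: the printed limits are not an error, and on that reading 5% is a fair description. But saying that a boundary can be calculated at any size does not schedule anyone to apply it, and the one scheduling sentence names three sizes.

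Second, 1.8% is still below 5%, and the plan sets no detection target. That is true when patients are counted. The loss is in sensitivity, and the rates used to show it are illustrative.

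Third, other oversight exists: SAE reporting to quality assurance within 24 hours with DMC review (7.3.3.1), quarterly SAE listings (7.3.3.3) and High Intensity Monitoring (7.0, 11.5). These limit the harm, but none is described as testing the 25% rate.

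Fourth, the inferred schedule is not unique at the start. A search from patient 5 gives the same printed limits with 4.6% overall. The printed Grade 5 rule, applied after every patient, attains 2.9% rather than 5%, and the same search would put a limit of 1 at the first two patients. These points affect the early rows of any table, not the conclusion.

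**Conclusion.** The concern holds. The stated 5% belongs to a check after every patient through 36 (4.7% attained), a schedule the text does not set. The looks it does set give 1.8% if they are the only ones, and leave patients 26 to 36 without a formal SAE look. Sections 6.2.1 and 10.3.4 also contradict each other on when the safety analysis occurs.

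At true rates of 40 to 50%, the three-look reading lowers the chance of flagging by about 17 to 21 percentage points. These figures rest on one counted event per patient, known at the look. Treatment runs up to 4 years (Section 4.1) and the plan gives no window for when a patient has been observed, so late events would lower the chance of flagging under either schedule. The shortfall is conservative for false alarms when patients are counted, and no efficacy conclusion depends on it. The plan should be corrected, but the point does not threaten the trial's main result.

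**What to change.** **Option 1, which keeps every printed limit.** State in 10.3.4 that the SAE boundary is applied after each patient through 36, give 4.7% as the attained probability, and print the table:

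| Patients | Flag at | Patients | Flag at |
|---|---|---|---|
| 4 | 4 | 21–23 | 11 |
| 5–7 | 5 | 24–26 | 12 |
| 8–9 | 6 | 27–28 | 13 |
| 10–12 | 7 | 29–31 | 14 |
| 13–14 | 8 | 32–34 | 15 |
| 15–17 | 9 | 35–36 | 16 |
| 18–20 | 10 | | |

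The cost is more frequent checking, unless it already happens, and a false-flag probability of 4.7% instead of 1.8%, still within the stated 5%. A lighter variant adds one look at 36 with limit 16 to the three printed looks (2.2%).

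**Option 2, if only three looks are kept.** Restate the 5% as 1.8%, which is wording only. Alternatively, use 8/15, 10/20 and 11/25, which changes two printed limits and attains 3.9%. Also say when the Grade 5 limit for 27 to 36 patients is checked.

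**In both cases.** Count patients with at least one drug-related SAE, define when a patient counts as observed, and reconcile the 18-month sentence in 6.2.1 with 10.3.4. If enrolment has ended, which the documents do not say, report which looks were made and the probabilities that apply to them.

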### 3.0 SELECTION OF SUBJECTS

The target population for this phase II study is patients with histologically confirmed (previously untreated) mantle cell lymphoma (MCL) who have achieved response (CR or PR) to intensive induction systemic chemotherapy (with or without ASCT). This will be a multicenter trial conducted at Northwestern University. Northwestern University will serve as the lead site and coordinating center for this study. Participating sites will include University of Utah, and Dana Farber d/b/a Massachusetts General Hospital.

A total of 36 *evaluable* subjects will be needed for this trial (defined as having received  $\geq$  1 complete cycle of treatment). Approximately 5 potentially eligible patients are seen per month, and it is anticipated that at least 2 per month will be accrued *once the protocol is open and enrolling at all sites*. Potential patients may be referred to the Principal Investigator (PI) at Northwestern University or to the local PI at each participating site.

Eligibility will be evaluated by the study team according to the following criteria. Eligibility waivers are not permitted. Subjects must meet all of the inclusion and exclusion criteria to be registered to the study. Study treatment may not begin until a subject is registered. Please refer to Section 11.4 for complete instructions regarding registration procedures.

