## 4.0 TREATMENT PLAN

### 4.1 Overview

Induction therapy will not be part of the protocol-specified treatment. Patients must have received four (4) or more cycles of R-CHOP (with or without alternating R-DHAP), R-Hyper-CVAD, or bendamustine + rituximab (all with or without auto SCT), with documented PR or CR by Cheson 2007 criteria. Within 14 days of study registration, patients will begin treatment with ibrutinib at a fixed dose of 560 mg PO daily. One cycle will be defined as 28 days. Patients may continue to receive cycles of ibrutinib therapy up to 4 years in the absence of progression of disease or intolerable toxicity, or patient preference (including withdrawal of consent).

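### The printed Grade 5 SAE limits give a false-alarm rate of 2.6% to 2.9%, not the stated 5%, so the rule is less sensitive than the plan implies

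*Combined protocol and SAP*

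**What the plan says.** Section 10.3.4 (Interim Analysis) sets two safety boundaries, both described as Pocock-type. The first is for drug-related SAEs at a reference rate of 25%, with limits of 9/15, 10/20 and 12/25. The second, at issue here, is for drug-related Grade 5 SAEs, which are deaths under section 7.2.2. For 36 patients and a 1% reference rate, the plan says that "there is a 5% probability of detecting an excess of Grade 5 SAEs when the SAE rate is at most 1"%. The limits are "at least 2 if the current sample size is 26 or less, and at least 3 if the current sample size is between" (the upper range runs from 27 to 36).

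The look schedule is less definite. Section 10.3.4 names formal evaluations after 15, 20 and 25 patients. It adds, after the 25% rule, that the boundary can be worked out for any interim sample size, and the Grade 5 limits are given for all sample sizes up to 36. The Amendment 5 entry in Appendix IV describes the monitoring as continuous. No look after 25 patients is scheduled in section 10.3.4.

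**The concern.** A monitoring committee will read the 5% as the rule's operating characteristic. With a 1% reference rate and only 36 patients the limits are very small whole numbers, so the attained rate can lie well away from the nominal one and has to be computed. If it lies well below 5%, false alarms are rarer than stated, but the chance of flagging a genuinely raised rate of drug-related death is also lower than a reader would assume. The printed rule also shows no limit of 1 at any sample size, although a boundary with the same tail probability at every sample size would be expected to have one for the first few patients.

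**Working it through.** **Inputs, all from section 10.3.4.** N = 36; reference rate p = 0.01; stated false-alarm probability 5%; limit 2 for n ≤ 26 and 3 for n = 27 to 36; named looks at 15, 20 and 25. Patients are taken as independent, with at most one Grade 5 event each.

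**Step 1. Identify the method.** The plan names a Pocock-type boundary without setting out its construction. I take it as the smallest count r at each n with P(X ≥ r | n, p) no larger than a common level, that level being the largest that keeps the overall crossing probability at or below 5%. Applied to the companion 25% rule, this returns exactly the plan's 9/15, 10/20 and 12/25 (overall 4.73%), which supports the construction.

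**Step 2. Apply it to the Grade 5 rule.** At p = 0.01:
- P(X ≥ 1 | n = 2) = 1 − 0.99² = 0.0199, and P(X ≥ 1 | n = 3) = 1 − 0.99³ = 0.0297.
- P(X ≥ 2 | n = 26) = 0.0277, and P(X ≥ 2 | n = 27) = 0.02975.
- P(X ≥ 3 | n = 36) = 0.0056.

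A common level of about 0.028 gives a limit of 1 at n = 1 to 2, 2 at n = 3 to 26, and 3 at n = 27 to 36. Its overall crossing probability is 4.42%. The next higher level extends the limit of 1 to n = 3 and gives 5.19%, so 4.42% is the largest value at or below 5%. The plan's step at 26/27 is reproduced; the limit of 1 at n = 1 to 2 does not appear in the plan.

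**Step 3. False-alarm rate of the printed limits, checked after every patient.**
- By n = 26: 1 − 0.99²⁶ − 26 × 0.01 × 0.99²⁵ = 1 − 0.7700 − 0.2022 = 0.0277.
- From n = 27 to 36, the count must reach 3. One event by n = 26 and at least two in the next ten: 0.2022 × 0.00427 = 0.00086. No event by n = 26 and at least three in the next ten: 0.7700 × 0.00011 = 0.00009. Sum 0.00095.
- Total: 0.0277 + 0.00095 = 0.0287, or 2.9%.

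**Step 4. Other look schedules.** At 15, 20 and 25 only, the limit is 2 each time, so the rate is P(X ≥ 2 | n = 25) = 0.0258, or 2.6%. Adding a look at 36 gives 2.69%. None of these schedules gives 5%.

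**Step 5. Detection.** Probability of crossing at any n, checked after every patient unless stated:

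| Limits | True rate 1% | 3% | 5% |
|---|---|---|---|
| As printed | 2.9% | 20% | 41% |
| As printed, looks at 15/20/25 only | 2.6% | 17% | 36% |
| Full Pocock-type (adds 1 at n = 1–2) | 4.4% | 22% | 44% |
| 2 through n = 35, 3 at n = 36 | 4.8% | 28% | 53% |
| 2 through n = 36 | 5.03% | 29% | 54% |

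With looks only at 15, 20 and 25, all these rules have a limit of 2 at each look, so they behave identically (2.6% at a true 1% rate).

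**The case against.** The strongest defence is that 5% is a ceiling. With counts this small no rule lands exactly on 5%, and the printed limits do not exceed it. That stands as far as validity goes: the error is on the conservative side. It does not rescue the wording, which gives 5% as the probability, and in safety monitoring unused error means lower sensitivity.

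Three stronger readings are tempting, and the documents do not support them.

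First, a reader might infer that raising the limit from 2 to 3 after patient 26 is itself the mistake. It is not. The Pocock-type construction puts the step exactly there, and the printed limits agree with that boundary at every n from 3 to 36, including all three named looks. The shortfall comes from the omitted limit of 1 at n = 1 to 2 (2.9% against 4.4%) and from discreteness (4.4% against 5%).

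Second, a reader might infer that a second drug-related death while the sample size is 27 to 36 would pass unnoticed. It would not cross this statistical limit. But section 7.3.3 requires every SAE to reach the quality assurance monitor within 24 hours and to be reviewed by the Data Monitoring Committee. Janssen must also be notified, and unanticipated, possibly related deaths go to the IRB. What is reduced is the sensitivity of one formal rule.

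Third, a reader might infer that the limit of 3 governs most of the exposure, because section 3.0 says "it is anticipated that at least 2 per month will be accrued" and treatment can run to 4 years. At 2 a month, 27 patients take 27/2 = 13.5 months. However, that rate applies only once all sites are open, and section 10.3.4 does not say whether the current sample size means patients enrolled, treated or observed. The timing cannot be fixed from the documents.

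**Conclusion.** The stated 5% and the printed Grade 5 limits do not agree. The printed limits attain 2.9% when checked after every patient and 2.6% at the three named looks. They reproduce the Pocock-type boundary only from n = 3 onward; the full boundary attains 4.4%. At a true 5% rate of drug-related death, with a check after every patient, detection is 41% as printed, 44% with the full boundary, and 53% to 54% with limits that use essentially all of the 5%.

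The figures assume independent patients and one event at most per patient. The 4.4% also assumes the Pocock-type construction in the working, which reproduces the plan's own 25% limits. The finding does not show that the printed limits are invalid or that any one alternative is required. It shows that the rule's description is wrong and that its sensitivity is lower than the description implies.

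**What to change.** In section 10.3.4, reconcile the stated 5%, the printed limits and the look schedule.

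- **At minimum:** keep the limits, restate their false-alarm probability at a 1% rate as about 2.9% (2.6% if checked only at 15, 20 and 25), and give the detection probabilities at one or two higher rates, for example 20% at a true 3% and 41% at a true 5% when checked after every patient. State when the Grade 5 limit is checked and what the current sample size counts.
- **If a rule that uses the stated 5% is wanted:** the sponsor and monitoring committee should choose among the full Pocock-type boundary (4.4%), a limit of 2 through n = 35 (4.8%) and a limit of 2 through n = 36 (5.03%). They should also state that the limit is checked beyond n = 25, since otherwise none of these changes anything.

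Each option has a drawback. The full Pocock-type boundary adds little detection (44% against 41%) and would flag on a single event in the first 2 patients. A limit of 2 through n = 35 leaves 3/36 in force once all 36 are counted. A limit of 2 through n = 36 is marginally above 5%. If the 3 replaced patients allowed for in the Study Summary are also counted, as section 6.2.1 does for toxicity, a limit of 2 carried to 39 patients gives 5.8%.

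The minimum change costs a sentence or two and alters no limit. The alternatives raise the false-alarm probability from 2.9% to between 4.4% and about 5%.
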